#### Expedited Reporting of AEs and Drug Exposure During Pregnancy

The following must be reported by the investigator on the NIS AE form from signing the informed consent onwards until the end of the study:

Type of Report	Timeline
All serious ADRs associated with Pradaxa®	immediately within 24 hours
All AEs with fatal outcome in patients exposed to Pradaxa®	immediately within 24 hours
All non-serious ADRs associated with Pradaxa®	7 calendar days
All pregnancy monitoring forms	7 calendar days

The same timelines apply if follow-up information becomes available for the respective events. In specific occasions the Investigator could inform the Sponsor upfront via telephone. This does not replace the requirement to complete and fax the NIS AE form.

#### Information required

For each reportable adverse event, the investigator should provide the information requested on the appropriate (e)CRF pages and the NIS AE form.

#### Reporting of related Adverse Events associated with any other BI drug

The investigator is encouraged to report all adverse events related to any BI drug other than the Pradaxa according to the local regulatory requirements for spontaneous AE reporting at the investigator's discretion by using the locally established routes and AE report forms. The term AE includes drug exposure during pregnancy, and, regardless of whether an AE occurred or not, any abuse, off-label use, misuse, medication error, occupational exposure, lack of effect, and unexpected benefit.

### **11.3 REPORTING TO HEALTH AUTHORITIES**

Adverse event reporting to regulatory agencies will be done by the MAH according to local and international regulatory requirements.

## **12. PLANS FOR DISSEMINATING AND COMMUNICATING STUDY RESULTS**

The rights of the investigator and of the sponsor with regard to publication of the results of this study are described in the investigator contract. As a general rule, no study results should be published prior to finalisation of the Study Report.

The results of this study may be published in a national journal and presented in regional or national congresses.

## **ANNEX 1. LIST OF STAND-ALONE DOCUMENTS**

Number	Title
<1>	Patient information and Informed Consent Form
<2>	Investigator List
<3>	Statistical Analysis Plan (SAP)
<4>	Data Management Plan (DMP)
<5>	Serious Adverse Event Report in Non-Interventional Studies (NIS (S)AE Form)
<6>	Pregnancy Monitoring Form

## ANNEX 2. ENCEPP CHECKLIST FOR STUDY PROTOCOLS

### Study title:

Non-Interventional, cross-sectional study to describe health-related quality of life among controlled and uncontrolled patients with nonvalvular atrial fibrillation on anticoagulants. RE-QUOL study.

### Study reference number:

1160-0280

Section 1: Milestones	Yes	No	N/A	Section Number
1.1 Does the protocol specify timelines for				
1.1.1 Start of data collection 				6
1.1.2 End of data collection 				6
1.1.3 Study progress report(s)				
1.1.4 Interim progress report(s)				
1.1.5 Registration in the EU PAS register				6
1.1.6 Final report of study results.				6

### Comments:

Study progress reports to Ethics committee and health authorities will be done annually according to spanish regulations.

Section 2: Research question	Yes	No	N/A	Section Number
2.1 Does the formulation of the research question and objectives clearly explain:				8
2.1.1 Why the study is conducted? (e.g. to address an important public health concern, a risk identified in the risk management plan, an emerging safety issue)				7
2.1.2 The objective(s) of the study?				8
2.1.3 The target population? (i.e. population or subgroup to whom the study results are intended to be generalised)				7
2.1.4 Which hypothesis(-es) is (are) to be tested?				
2.1.5 If applicable, that there is no a priori hypothesis?				

### Comments:

Exploratory study

 Date from which information on the first study is first recorded in the study dataset or, in the case of secondary use of data, the date from which data extraction starts.

 Date from which the analytical dataset is completely available.

Section 3: Study design	Yes	No	N/A	Section Number
3.1 Is the study design described? (e.g. cohort, case-control, cross-sectional, new or alternative design)				9.1
3.2 Does the protocol specify whether the study is based on primary, secondary or combined data collection?				9.4
3.3 Does the protocol specify measures of occurrence? (e.g. incidence rate, absolute risk)				
3.4 Does the protocol specify measure(s) of association? (e.g. relative risk, odds ratio, excess risk, incidence rate ratio, hazard ratio, number needed to harm (NNH) per year)				
3.5 Does the protocol describe the approach for the collection and reporting of adverse events/adverse reactions? (e.g. adverse events that will not be collected in case of primary data collection)				11

Comments:

Descriptive study. No measures of occurrence or measures of association are performed

Section 4: Source and study populations	Yes	No	N/A	Section Number
4.1 Is the source population described?				9.2
4.2 Is the planned study population defined in terms of:				
4.2.1 Study time period?				9.1
4.2.2 Age and sex?				9.2
4.2.3 Country of origin?				9.2
4.2.4 Disease/indication?				9.2
4.2.5 Duration of follow-up?				
4.3 Does the protocol define how the study population will be sampled from the source population? (e.g. event or inclusion/exclusion criteria)				9.2

Comments:

Cross-sectional study. No follow-up is carried out

Section 5: Exposure definition and measurement	Yes	No	N/A	Section Number
5.1 Does the protocol describe how the study exposure is defined and measured? (e.g. operational details for defining and categorising exposure, measurement of dose and duration of drug exposure)				9.3
5.2 Does the protocol address the validity of the exposure measurement? (e.g. precision, accuracy, use of validation sub-study)				

Section 5: Exposure definition and measurement	Yes	No	N/A	Section Number
5.3 Is exposure classified according to time windows? (e.g. current user, former user, non-use)				9.3
5.4 Is exposure classified based on biological mechanism of action and taking into account the pharmacokinetics and pharmacodynamics of the drug?				

Comments:

Observational study. Patients treated as per routine clinical practice.

Section 6: Outcome definition and measurement	Yes	No	N/A	Section Number
6.1 Does the protocol specify the primary and secondary (if applicable) outcome(s) to be investigated?				9.3
6.2 Does the protocol describe how the outcomes are defined and measured?				9.3
6.3 Does the protocol address the validity of outcome measurement? (e.g. precision, accuracy, sensitivity, specificity, positive predictive value, prospective or retrospective ascertainment, use of validation sub-study)				
6.4 Does the protocol describe specific endpoints relevant for Health Technology Assessment? (e.g. HRQoL, QALYs, DALYS, health care services utilisation, burden of disease, disease management)				9.3

Comments:

Descriptive outcomes

Section 7: Bias	Yes	No	N/A	Section Number
7.1 Does the protocol describe how confounding will be addressed in the study?				
7.1.1. Does the protocol address confounding by indication if applicable?				
7.2 Does the protocol address:				
7.2.1. Selection biases (e.g. healthy user bias)				9.2
7.2.2. Information biases (e.g. misclassification of exposure and endpoints, time-related bias)				
7.3 Does the protocol address the validity of the study covariates?				

Comments:

This study is only descriptive

Section 8: Effect modification	Yes	No	N/A	Section Number
---------------------------------------	------------	-----------	------------	-----------------------

Section 8: Effect modification	Yes	No	N/A	Section Number
8.1 Does the protocol address effect modifiers? (e.g. collection of data on known effect modifiers, sub-group analyses, anticipated direction of effect)				

Comments:

This study is only descriptive

Section 9: Data sources	Yes	No	N/A	Section Number
9.1 Does the protocol describe the data source(s) used in the study for the ascertainment of:				
9.1.1 Exposure? (e.g. pharmacy dispensing, general practice prescribing, claims data, self-report, face-to-face interview)				9.4
9.1.2 Outcomes? (e.g. clinical records, laboratory markers or values, claims data, self-report, patient interview including scales and questionnaires, vital statistics)				9.3
9.1.3 Covariates?				
9.2 Does the protocol describe the information available from the data source(s) on:				
9.2.1 Exposure? (e.g. date of dispensing, drug quantity, dose, number of days of supply prescription, daily dosage, prescriber)				9.3
9.2.2 Outcomes? (e.g. date of occurrence, multiple event, severity measures related to event)				9.3
9.2.3 Covariates? (e.g. age, sex, clinical and drug use history, co-morbidity, co-medications, lifestyle)				
9.3 Is a coding system described for:				
9.3.1 Exposure? (e.g. WHO Drug Dictionary, Anatomical Therapeutic Chemical (ATC) Classification System)				
9.3.2 Outcomes? (e.g. International Classification of Diseases (ICD)-10, Medical Dictionary for Regulatory Activities (MedDRA))				
9.3.3 Covariates?				
9.4 Is a linkage method between data sources described? (e.g. based on a unique identifier or other)				9.2

Comments:

Coding system for exposure and outcomes will be described in SAP

Section 10: Analysis plan	Yes	No	N/A	Section Number
10.1 Is the choice of statistical techniques described?				9.7
10.2 Are descriptive analyses included?				9.7
10.3 Are stratified analyses included?				

Section 10: Analysis plan	Yes	No	N/A	Section Number
10.4 Does the plan describe methods for adjusting for confounding?				
10.5 Does the plan describe methods for handling missing data?				9.7
10.6 Is sample size and/or statistical power estimated?				9.5

Comments:

This study is only descriptive

Section 11: Data management and quality control	Yes	No	N/A	Section Number
11.1 Does the protocol provide information on data storage? (e.g. software and IT environment, database maintenance and anti-fraud protection, archiving)				9.6
11.2 Are methods of quality assurance described?				9.8
11.3 Is there a system in place for independent review of study results?				

Comments:

Observational study of routine clinical practice.

Section 12: Limitations	Yes	No	N/A	Section Number
12.1 Does the protocol discuss the impact on the study results of:				
12.1.1 Selection bias?				9.2
12.1.2 Information bias?				
12.1.3 Residual/unmeasured confounding? (e.g. anticipated direction and magnitude of such biases, validation sub-study, use of validation and external data, analytical methods)				
12.2 Does the protocol discuss study feasibility? (e.g. study size, anticipated exposure, duration of follow-up in a cohort study, patient recruitment)				9.2

Comments:

This study is only descriptive

Section 13: Ethical issues	Yes	No	N/A	Section Number
13.1 Have requirements of Ethics Committee/ Institutional Review Board been described?				10.1
13.2 Has any outcome of an ethical review procedure been addressed?				
13.3 Have data protection requirements been described?				10.1

Comments:

--

Section 14: Amendments and deviations	Yes	No	N/A	Section Number
14.1 Does the protocol include a section to document amendments and deviations?				5

Comments:

--

Section 15: Plans for communication of study results	Yes	No	N/A	Section Number
15.1 Are plans described for communicating study results (e.g. to regulatory authorities)?				12
15.2 Are plans described for disseminating study results externally, including publication?				12

## **ANNEX 3. ADDITIONAL INFORMATION**

### **Spanish adaptation of the Sawicki questionnaire:**

1. Su tratamiento le hace sentir preocupado o estresado	1	2	3	4	5	6
2. El esfuerzo por controlar su coagulación sanguínea le produce molestias cuando está fuera de casa	1	2	3	4	5	6
3. Su tratamiento le limita para organizar su tiempo libre como quiere	1	2	3	4	5	6
4. Está insatisfecho con la cantidad de tiempo que invierte en controlar su coagulación	1	2	3	4	5	6
5. Cree que ha aprendido a controlar su tratamiento	1	2	3	4	5	6
6. El riesgo de hacerse heridas le limita para llevar a cabo sus tareas domésticas	1	2	3	4	5	6
7. Evita realizar ciertas actividades (p. ej. Montar en bicicleta) por el riesgo de accidentes	1	2	3	4	5	6
8. Su tratamiento preocupa a sus familiares	1	2	3	4	5	6
9. Puede afrontar los problemas que surgen relacionados con su tratamiento	1	2	3	4	5	6
10. Le preocupa su salud en el futuro	1	2	3	4	5	6
11. Tiene miedo de realizar ejercicio por el miedo de hacerse una herida	1	2	3	4	5	6
12. Está insatisfecho con el tiempo que le lleva conseguir los resultados	1	2	3	4	5	6
13. Le preocupa que su tratamiento pudiera acortar su vida	1	2	3	4	5	6
14. Le disgusta tener que planear sus actividades con antelación	1	2	3	4	5	6
15. Le preocupa la incertidumbre que siente mientras espera los resultados	1	2	3	4	5	6
16. Ve menos a sus amigos desde que sigue este tratamiento	1	2	3	4	5	6
17. Evita salir de vacaciones porque es incapaz de conocer los efectos negativos que tienen los diferentes alimentos en su tratamiento	1	2	3	4	5	6
18. Está bien informado de lo que debe hacer para conseguir unos resultados dentro de los límites adecuados	1	2	3	4	5	6
19. Se siente dependiente de su medicación anticoagulante	1	2	3	4	5	6
20. Evita viajar porque tiene miedo de no recibir tratamiento adecuado en el caso de que sus resultados estén demasiado altos o bajos	1	2	3	4	5	6

Proprietary confidential information © 2017 Boehringer Ingelheim International GmbH or one or more of its affiliated companies

21. Está harto de la cantidad de tiempo que pierde en el médico	1	2	3	4	5	6
22. Practicaría más deporte si no tomara anticoagulantes	1	2	3	4	5	6
23. Tiene problemas en el trabajo por sus frecuentes faltas a causa del tratamiento	1	2	3	4	5	6
24. Está seguro de poder controlar su tratamiento	1	2	3	4	5	6
25. Tiende a preocuparse por las cosas	1	2	3	4	5	6
26. A pesar de las visitas habituales al médico, cómo se siente de limitado	1	2	3	4	5	6
27. Le molesta que mucha gente no comprenda los problemas relacionados con su tratamiento	1	2	3	4	5	6
28. Cuando va al dentista o a otros médicos. Está preocupado por si no saben lo suficiente sobre la anticoagulación	1	2	3	4	5	6
29. Su tratamiento ha afectado a su vida sexual	1	2	3	4	5	6
30. Le molesta ser tratado como un inválido	1	2	3	4	5	6
31. Está preocupado por los efectos secundarios de su tratamiento anticoagulante	1	2	3	4	5	6
32. Le preocupa la reacción de otras personas ante su tratamiento	1	2	3	4	5	6

**Opciones de respuesta**

1=Nada

2=Muy poco

3=Poco

4=Algo

5=Bastante

6=Mucho

---

# REQUOL Study

## GLOSSARY

AF	Atrial Fibrillation
BMI	Body mass index
CHA2DS2-VASc	Congestive heart failure, Hypertension, Age, Diabetes mellitus, Stroke/TIA/thrombo-embolism, Vascular disease, Sex Female SCORE
CRF	Case report form
DOAC	Direct oral anticoagulant
HAS-BLED	Hypertension, Abnormal renal and liver function, Stroke, Bleeding, Labile INR, Elderly, Drugs or alcohol SCORE
HRQoL	Health-related quality of life
IC	Inclusion criterion
Max	Maximum
Min	Minimum
N	Number of patients
NVAF	Non-valvular atrial fibrillation
Q1	First quartile
Q3	Third quartile
SD	Standard deviation
VKA	Vitamin K antagonists

# **REQUOL Study**

## **1 INTRODUCTION**

Atrial fibrillation (AF) affects 1-2% of the general population, but especially patients aged from 80-85 years, in whom the prevalence rate can be as high as 16%. The first oral anticoagulants to prevent the risk of thromboembolic episodes in AF were vitamin K antagonists (VKA), warfarin and acenocoumarol. Management of these drugs continues to be problematic, as they require routine clotting monitoring, clinical supervision and ongoing patient education, affecting their daily habits and, hence, their quality of life. Data also shows that 80% of patients continue to receive acenocoumarol in Spain, 44-59% of them with an international normalized rate (INR) within the therapeutic range, and a mean time in therapeutic range (TTR) of 64%.

Direct oral anticoagulants (DOAC) maintain the beneficial effects of anticoagulant therapy and can increase patient perception of quality of life, as they do not require the strict monitoring necessary for VKAs. On the other hand, maintaining a stable anticoagulation level with DOACs eliminates the risk of uncontrolled patients and prevents increased numbers of doctor visits for this reason. In theory, this would have positive implications for quality of life. However, the evidence provided by the quality of life study does not appear to show that AF leads to major reductions in quality of life. In this respect, the cross-sectional study by Roalfe et al. in 1762 patients of more than 75 years of age with AF reached the conclusion that, in the absence of comorbidities, chronic AF has little impact on generic quality of life. This suggests that treatment strategies should focus on the prevention of complications such as stroke, so further studies are required on anticoagulant therapy and its impact on quality of life.

HRQoL was evaluated in a subgroup of the RE-LY population to determine the effect of choice of anticoagulant during a stable treatment phase in the first year of the study, in patients with no significant events such as stroke or important haemorrhages. HRQoL was evaluated by the EQ-5D questionnaire, a generic healthcare assessment tool. In one year, all the patients taking anticoagulants with no significant events presented a stable HRQoL. The scores obtained by dabigatran and warfarin were comparable. There are insufficient data regarding HRQoL in controlled and uncontrolled patients treated with oral anticoagulants.

This study was designed to describe HRQoL in uncontrolled patients with NVAF treated with conventional VKAs and controlled patients receiving a VKA or DOAC.

Given that the type of patients to be enrolled in this study are those seen in internal medicine, as they are elderly or chronic patients, largely hospitalised, polymedicated and with a high risk

## **REQUOL Study**

of haemorrhage and thromboembolism, this study will provide information about the HRQoL of these patients in relation to their anticoagulation status (controlled or uncontrolled).

### **2 OBJECTIVE AND DESIGN**

#### **2.1 Objectives of the analytical plan**

This document presents a proposed analytical plan for the final statistical analysis of the REQUOL study.

The analytical plan proposed below details the aspects to be learned about the study and the statistical methods of analysis to be used and applied to the collected data to comply with the primary objective and the secondary objectives.

#### **2.2 Primary study objective**

To describe HRQoL in uncontrolled patients treated with VKA and controlled patients treated with VKA or DOAC.

#### **2.3 Secondary objectives**

To describe the profile of uncontrolled patients.

#### **2.4 Study design**

Cross-sectional, multicentre, observational study.

#### **2.5 Study population**

The patients to be included will present NVAF and receive the same anticoagulant treatment (VKA or DOAC) for at least 6 months and up to 2 years. They will be seen in internal medicine departments.

In all, it is expected that approximately 330 patients will be included in the controlled group and 170 in the uncontrolled group.

#### **2.6 Inclusion criteria**

Patients will be included in the study if they meet all the following criteria:

1. The patient is willing to participate and grants his or her informed consent to participate in the study in writing.
2. The patient is at least 18 years old.
3. The patient has a diagnosis of NVAF.

## **REQUOL Study**

4. The patient has been receiving the same anticoagulant treatment (VKA or DOAC) for at least 6 months and no more than 2 years.
5. If he/she receives treatment with VKA, availability of TRT% in previous analytical records or sufficient INR measures to calculate same.

### **2.7 Exclusion criteria**

Patients will be excluded from the study if they meet 1 or more of the following criteria:

1. Participation in any clinical trial of a drug or medical device.
2. Contraindications for the use of DOAC or VKA as described in the summary of product characteristics.

## **3 STATISTICAL ANALYSIS METHODS**

Following are the analytical methods to be used both to attain the study's objectives and to describe the variables.

The quantitative variables will be described with centralisation and dispersion measures (mean, median, SD (standard deviation), Q1 (first quartile), Q3 (third quartile), minimum and maximum). The qualitative variables are described by absolute and relative frequencies.

In the descriptive analysis of the qualitative variables there will be two percentage columns, the total (%) and valid (% valid) percentages, in other words the sum of valid responses plus missing values and the percentage of the total valid responses.

The data shall be analysed by SPSS v18.0 or later.

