## **9.7 DATA ANALYSIS**

Analyses will be performed by Boehringer Ingelheim's designees. The analysis population will consist of all eligible patients (i.e. all patients fulfilling all inclusion criteria and no exclusion criteria).

In this non-interventional study, cross-sectional data at study visit will be collected for non-valvular AF patients with a VKA or DOAC therapy. Once the study has been completed and all data from the last patient have been recorded, the database will be closed and statistical analysis will be performed.

The proposed methods for statistical analysis presented below are a summary of the methods that will be applied in the study to analyze the data collected and to answer the study objectives. Missing data will not be imputed and will be left as lost.

Summary statistics for continuous variables will include the N, mean, standard deviation, minimum, Q1 (lower quartile), median, Q2 (upper quartile), and maximum value; tabulations of categorical variables will present all possible categories and will display the number of observations per category as well as percentages. Estimates will be presented with 95% confidence intervals for the variables of interest. Additional details of the planned analysis will be provided in the statistical analysis plan (SAP).

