## **8 ANALYSIS OF THE OBJECTIVES**

### **8.1 Primary objective**

***To describe HRQoL in uncontrolled patients treated with VKA and controlled patients treated with VKA or DOAC.***

All the analyses in this section shall be performed for the controlled, uncontrolled and total populations.

Quality of Life shall be based on the patients' assessments, by completing the Sawicki questionnaire during the single study visit. This questionnaire includes 32 items grouped in 5 dimensions: overall treatment satisfaction, self-efficacy, strained social disturbances, daily hassles and distress. The highest scores show less quality of life (validated adapted Spanish questionnaire). The response options for each question are: 1=Not at all, 2=Very slightly, 3=Slightly, 4=Moderately, 5=Quite a lot, 6=Very much. The responses correspond to a quantitative scale from 1 to 6.

Reference: Sanchez GR, Yanes BM, Cabrera MA, Ferrer Garcia-Borras JM, Alvarez NR, Barrera LE. [Cross-cultural adaptation of a questionnaire for measuring the quality of life of patients taking oral anticoagulants]. *Aten Primaria* 2004;34(353):353-9.

The categorical variable to be described is: N and (%):

- Number of patients who completed the questionnaire

The summary score for each dimension is calculated by dividing the total score of the items that comprise each dimension by the number of items included in that dimension (arithmetical mean of the items in question).

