## **REQUOL Study**

26. Despite regular visits to the doctor, I feel limited
27. I am annoyed that many people do not understand the problems related to my treatment
28. When I go to the dentist or other doctors. I am concerned that they might not know enough about anticoagulation
29. The treatment has affected my sex life
30. I dislike being treated like an invalid
31. I am worried about the side effects of my anticoagulant treatment
32. I am worried about other people's reactions to my treatment

The descriptive statistic (Mean, SD, Median, Q1, Q3, Min, Max) will be shown for each of the previously calculated dimensions:

- Treatment Satisfaction
- Self-efficacy
- Stress
- Limitations
- Social disturbances

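### Must the SAP change because its Sawicki tables list no N and it gives no rule for blank items?

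*SAP*

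**What the plan says.** Protocol 9.7 sets the reporting standard: "Summary statistics for continuous variables will include the N, mean, standard deviation", followed by the range, quartiles and median. It also promises 95% confidence intervals for the variables of interest and leaves further detail to the SAP. On missing values it states: "Missing data will not be imputed and will be left as lost". SAP 3.1 says much the same, that missing values do not count.

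SAP 3 summarises quantitative variables by central tendency and "dispersion measures (mean, median, SD (standard deviation), Q1 (first quartile), Q3 (third quartile), minimum and maximum". N is not in that list. A display of missing values is specified only for categorical variables: "In the descriptive analysis of the qualitative variables there will be two percentage columns, the total (%) and valid (% valid) percentages". SAP 8.1 puts the Sawicki answers on the quantitative side ("The responses correspond to a quantitative scale from 1 to 6") and asks for the same seven statistics for each item. The same set "will be shown for each of the previously calculated dimensions". No confidence interval is listed. The one count specific to the questionnaire is "Number of patients who completed the questionnaire", and completion is not defined.

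A dimension score is obtained by "dividing the total score of the items that comprise each dimension by the number of items included in that dimension", which SAP 8.1 also describes as the arithmetic mean of those items. Protocol 9.7.1 gives the same formula. Neither document mentions a partly answered dimension.

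**The concern.** The Sawicki scores are the primary outcome. Read alone, the SAP would give means and SDs without the number of patients behind them. The analysis set is all eligible patients, and eligibility does not require a completed questionnaire, so the group size is not necessarily that number. One overall count of completers cannot vary by item or dimension.

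The scoring gap seems to make this worse. A dimension with a blank item could be averaged over the answered items or set to missing, and N differs between the two.

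There is also a route to unequal loss. Protocol 9.9 notes that the questionnaire was designed for VKA patients, and Protocol 7 that DOACs do not need the same monitoring. Items 4, 12 and 15, half of the Satisfaction dimension, concern time spent on clotting control or waiting for results. All DOAC patients are in the controlled group. If they skip those items, the controlled Satisfaction mean could lose DOAC patients and shift towards the VKA score, and a reader would not see it.

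**Working it through.** **The plan's own figure.** The only computed figure is the table of Clopper-Pearson interval widths in Protocol 9.5. All ten widths reproduce within 0.01 percentage points (for example 9.594 against 9.60 for 17 of 170, and 11.050 against 11.05 for 50% of 330). The table concerns proportions, and the present point does not depend on it.

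**Is N withdrawn?** Protocol 9.7 names N. SAP 3 lists measures of location and spread, and N is neither. No SAP sentence says that N will be left out or that the protocol list is replaced. The two lists can both be met by printing N. The same holds for the 95% interval.

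**Which scoring readings survive?** Take one blank item with every other item in the dimension scored 4. With k items:

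| Dimension | k | Blank as 0: 4(k−1)/k | Mean of answered | Set to missing |
|---|---|---|---|---|
| Self-efficacy | 4 | 3.00 | 4.00 | no score |
| Social disturbances | 5 | 3.20 | 4.00 | no score |
| Satisfaction (inverted scores) | 6 | 3.33 | 4.00 | no score |
| Limitations | 7 | 3.43 | 4.00 | no score |
| Stress | 10 | 3.60 | 4.00 | no score |

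The zero column fills the blank with a value off the 1 to 6 scale, which the no-imputation statements exclude. A mean of answered items equals filling the blank with the patient's own mean. A strict reading of Protocol 9.7 excludes that too and leaves the dimension missing. SAP 3.1 leaves some room for the mean of answered items.

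**Does reporting N reveal the rule?** If any blank makes the dimension missing, its N cannot exceed the smallest N among its items. If the score is a mean of answered items with no minimum, its N cannot fall below the largest item N. As soon as one patient has a partly answered dimension, the two cases differ. Item and dimension Ns, as Protocol 9.7 requires, therefore show which of these two rules was used and how many patients were lost.

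**How large could the difference be?** The inputs are assumptions: d is the DOAC share of the 330 controlled patients, and f the share of DOAC patients with a blank in items 4, 12 or 15. There are no other blanks, and DOAC patients with and without blanks score alike. Under set-to-missing:

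- N = 330(1 − df)
- DOAC share of scored patients = d(1 − f)/(1 − df)
- Gap between rules = d minus that share, per 1-point VKA-DOAC difference

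| f | d | N | DOAC share scored | Gap |
|---|---|---|---|---|
| 0.10 | 0.3 / 0.5 / 0.7 | 320 / 314 / 307 | 0.278 / 0.474 / 0.677 | 0.022 / 0.026 / 0.023 |
| 0.50 | 0.3 / 0.5 / 0.7 | 280 / 248 / 215 | 0.176 / 0.333 / 0.538 | 0.124 / 0.167 / 0.162 |

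With an assumed SD of 1.0, the 95% half-width is 0.108 at N = 330 and 0.135 at N = 215.

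**Is that range stable?** Take d = f = 0.5, VKA patients at 4 and DOAC patients without blanks at 5.

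- DOAC patients with blanks also at 5: mean of answered gives 0.5×4 + 0.5×5 = 4.50; set-to-missing gives (0.5×4 + 0.25×5)/0.75 = 4.33. Gap +0.17.
- DOAC patients with blanks at 4: mean of answered gives 0.5×4 + 0.25×5 + 0.25×4 = 4.25; set-to-missing is again 4.33. Gap −0.08.

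The size halves and the sign changes with an assumption that the documents cannot settle.

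**The case for a change.** The best case for a change is that a primary-outcome score should have its missing-item rule written down before the data are seen, and that a few SAP lines would do it. The wording gap is real. The SAP asks for N with percentages for categorical variables, so its absence from the quantitative lists is a genuine slip. With an assumed 2% independent blank rate per item, complete Stress scores would number 170×0.98^10 = 139 of 170 and 330×0.98^10 = 270 of 330, so N could vary by dimension even without any DOAC effect.

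Other parts of the case are weaker. The unequal-loss route needs DOAC patients to leave items blank when the form offers the lowest answer, not at all, and it needs no one else to skip anything. Items 23 (work absences) and 29 (sex life) could be skipped in either group. It also needs blanks to go uncorrected. Protocol 9.6 has staff entering data directly in the eCRF with immediate feedback on missing values, and nothing says the patient has left by then.

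A single-patient example can suggest a full point at stake. With inverted scores of 4 on items 14, 21 and 27, answering not at all on 4, 12 and 15 gives (3×6 + 3×4)/6 = 5.00, and leaving them blank gives (4+4+4)/3 = 4.00. That compares answering with not answering, not one scoring rule with the other. A mean-of-answered rule would still score this patient 4.00.

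A half-answered threshold would also be a convention from outside the documents, and it may conflict with the protocol's no-imputation statement.

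**Conclusion.** No change is needed. The missing N is a drafting slip that Protocol 9.7 already covers. The blank-item gap is one an analyst fills sensibly: setting the dimension to missing is the closest reading of the no-imputation statements, a mean of answered items is the other defensible descriptive score, and the N that the protocol requires shows which was used.

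The study is descriptive, no test is affected, and complete questionnaires score identically. The documents support no numerical effect. The 0.02 to 0.17 range rests on assumed DOAC shares of 30 to 70%, assumed blank rates of 10 to 50% and equal scores in DOAC patients with and without blanks. Relaxing the last assumption alone can move 0.17 to −0.08. The conclusion assumes that the analyst follows Protocol 9.7 in reporting N and intervals, which nothing in the SAP prevents.
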